11.6.4. Audiometry Assessments

Descriptive summary statistics for audiometric assessments of air and bone conduction thresholds at each frequency will be provided by treatment group and study visit. In addition, the PTA computed as the average air conduction threshold for the 500, 1000, and 2000 Hz will also be calculated.

Air-Bone Gap assessments at each frequency for treatment group and study visit will be tabulated as the proportion of subjects with air minus bone conduction thresholds of:

- 1. $\leq 10 \text{ dB or}$
- 2. > 10 dB.

All audiometry assessments will be tabulated separately for the treated and untreated ear.

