1. BACKGROUND

Meniere's disease is an idiopathic syndrome of endolymphatic hydrops (Committee on Hearing and Equilibrium, 1995). It is associated with a distinct pattern of clinical symptoms comprised of vertigo, hearing loss, tinnitus and aural fullness. It is more frequently unilateral than bilateral. Episodic vertigo is considered the most prominent symptom, with episodes typically lasting at least 20 minutes and resulting in significant patient morbidity. The diagnosis is primarily a clinical one, since there are no specific diagnostic tests for Meniere's disease. The disease is known to wax and wane, but eventually results in irreversible sensorineural hearing loss at all frequencies in the affected ear. While the pathogenesis of Meniere's disease has not been elucidated, one well-accepted mechanism involves the dysregulation of labyrinth fluid volume/ion balance resulting in endolymphatic hydrops (Shea, 1993). The increase in fluid volume and consequent increased labyrinth pressure may then be expressed as the Meniere's spectrum of symptoms.

There is no cure for Meniere's disease. Treatment tends to focus on relieving the vertigo symptoms, where it is hypothesized that reducing inner ear fluid volume will relieve the hydrops and associated clinical picture. It is for this reason that many subjects are initially started on low salt diets and diuretics (Barritt, 2008). A number of medical systemic treatments are also used to relieve Meniere's disease symptoms, including but not limited to antihistamines, anticholinergics, phenothiazines, benzodiazepines, and corticosteroids; however, these interventions are often inadequate in relieving the symptoms of Meniere's disease. A device that generates low-pressure pulses, the Meniett® device, is indicated for the symptomatic treatment of Meniere's disease. However, the device is not widely used and is not currently considered standard of care (Kim et al, 2005). Surgical decompression may be attempted in severe cases unresponsive to medical intervention, but surgical outcomes are frequently unsatisfactory. Finally, patients with unresponsive disease may undergo chemical or surgical neuroablation, resulting in symptom relief at the cost of destruction of the 8th cranial nerve. Thus, there continues to be an unmet medical need for therapies to address this debilitating disease.

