11.6.2. Vital Signs and Laboratory Parameters

The analysis of vital signs and laboratory parameters will include descriptive statistics for the change from baseline to the endpoint visit, change from baseline for each visit (vital signs only). Where appropriate, analyses will also include shifts from baseline to the endpoint visit. For laboratory values, the normal ranges will be used to determine the classifications. Values below the normal range will be classified as low, values above the normal range will be classified as high, and values within the normal range will be classified as normal.

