11.6.5. Tympanometry

Shift tables representing the proportion of subjects with changes in their tympanogram from baseline to each post-baseline study visit will be calculated for each treatment group. Tympanogram changes will include both the type of tympanogram (A, B-small volume and/or normal, B-large volume, or C), as well as, whether the tympanogram was judged to be normal or abnormal.

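### Section 11.6.4 specifies no change from baseline for audiometry and no count of subjects whose hearing declined, so a treated-ear loss in a small minority would be unlikely to show in the planned audiometry tables

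*Combined protocol and SAP*

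**What the plan says.** Protocol Section 11.6.4 plans three audiometry summaries:

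- Thresholds: "Descriptive summary statistics for audiometric assessments of air and bone conduction thresholds at each frequency will be provided by treatment group and study visit".
- PTA: "the PTA computed as the average air conduction threshold for the 500, 1000, and 2000 Hz will also be calculated".
- Air-bone gap: "Air-Bone Gap assessments at each frequency for treatment group and study visit will be tabulated as the proportion of subjects" in two classes, at most 10 dB and more than 10 dB.

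It then says "All audiometry assessments will be tabulated separately for the treated and untreated ear". The section mentions neither a comparison with baseline nor a criterion for decline.

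The other measures in Section 11.6 are treated differently:

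- Vital signs and laboratory (11.6.2): "descriptive statistics for the change from baseline to the endpoint visit", with shifts where appropriate.
- Otoscopy (11.6.3): number and proportion of subjects whose classification changed from baseline, where relevant.
- Tympanometry (11.6.5): "Shift tables representing the proportion of subjects with changes in their tympanogram from baseline to each post-baseline study visit".

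The data for a change analysis are collected. Section 8.3.4 requires air and bone audiograms at five frequencies at every visit, and Section 8.1.3 places the Visit 2 audiogram before dosing. Section 11.6 makes the safety tabulations descriptive. The introduction to Section 11 leaves further methodological detail to a SAP, but the supplied text contains no SAP section on audiometry.

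**The concern.** The secondary objective is to describe the safety of an injection placed next to the round window niche. The Background says that the disease itself "eventually results in irreversible sensorineural hearing loss at all frequencies in the affected ear". Audiometry is the only planned safety test of hearing function, yet within Section 11.6 it is the ear assessment analysed without reference to the subject's own baseline.

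Two features combine. The air-bone gap responds to conductive change only, so it misses the type of loss that the Background describes. By-visit summaries of raw thresholds mix any decline with the differences in hearing that subjects bring into the trial. Inclusion criterion 4 can be met by asymmetry or by investigator judgment and sets no upper limit on loss, and Section 11.3 makes degree of hearing loss a subgroup. The arms could then look alike in these tables although some treated ears had worsened.

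**Working it through.** The plan gives no audiometry figure to reproduce. Its power statement (Section 11.1) concerns vertigo days only. The one input taken from the documents is 80 subjects per arm. The SDs, the fraction affected, the size of the loss and the 15 dB cut below are all assumptions for illustration.

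**1. Air-bone gap.** Gap = air threshold minus bone threshold. Take air 40 dB and bone 35 dB: the gap is 5 dB. After a 30 dB sensorineural loss, air is 70 and bone 65: the gap is still 5 dB. The subject stays in the class of at most 10 dB.

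**2. By-visit means, simple form.** If a fraction f of treated ears in one arm loses D dB, that arm's mean moves by f × D. With f = 0.10 (8 of 80) and D = 20, the shift is 2 dB. The SE of the between-arm difference is SD × √(2/80):

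| Between-subject SD (assumed) | SE | 2 dB in SE units |
|---|---|---|
| 15 dB | 2.37 dB | 0.84 |
| 20 dB | 3.16 dB | 0.63 |
| 25 dB | 3.95 dB | 0.51 |

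**3. Wider range.** Losses in a subset also widen the spread in that arm: SD_active² = SD² + f(1 − f)D², and SE = √((SD_active² + SD²)/80). The chance of crossing a two-sided 0.05 line in the harmful direction is Φ(fD/SE − 1.96). Safety is not tested in this trial, so this serves only as a yardstick of visibility.

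For per-subject change, assume that the SD of change is 7-10 dB. The mean-change column uses the same formulas with that SD. For the decline count, take 15 dB as an illustrative cut. The placebo proportion is p0 = 1 − Φ(15/SD), which is 0.016 or 0.067. The active proportion is f × [1 − Φ((15 − D)/SD)] + (1 − f) × p0. The two proportions are compared with 80 per arm. The ranges cover D = 20-30 dB.

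| Fraction affected | By-visit means (SD 15-25) | Mean change | Proportion declining ≥15 dB |
|---|---|---|---|
| 5% | 4-9% | 9-20% | 11-34% |
| 10% | 7-21% | 21-52% | 26-71% |
| 20% | 17-60% | 60-93% | 66-98% |
| 30% | 31-89% | 89-99.7% | 91-100% |

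At 10% affected, a decline table would show about 7-12 active subjects against 1-5 placebo subjects. The planned tables show no such count.

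**4. Sensitivity to placebo decline.** Fisher exact, two-sided, 80 per arm, with 8 decliners on OTO-104:

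| Placebo decliners | p |
|---|---|
| 0 | 0.0065 |
| 1 | 0.034 |
| 2 | 0.098 |
| 3 | 0.21 |
| 5 | 0.56 |

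**The case against.** Four points can be made for the plan.

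- **The SAP may add the analysis.** Section 11 describes general methods and promises detail before unblinding. A reader might infer that the trial will have no change analysis at all. The documents do not support that: they show only that the protocol section names none. Even so, the protocol does specify change or shift for the neighbouring measures, so its silence on audiometry is more than a level-of-detail choice.
- **Mean change can be recovered.** Subtracting visit means within an arm gives mean change, exactly if data are complete, and the untreated ear offers a comparison. This stands, so it would be too strong to say that a decline could not show. The subtraction gives neither the SD of change nor the number of decliners, and it is the count that describes a loss confined to a few subjects.
- **Adverse events.** A reader might infer that adverse-event tables would miss every decline. They would not. Sections 9 and 9.1 make worsening of an existing condition an adverse event, events are tabulated, and Section 14.7 has ear and labyrinth events reviewed blinded at least every other month. However, an abnormal test result counts only under the four conditions in Section 9.1. Reporting is voluntary or prompted by non-directed questions (9.2.1), and no audiometric decline is predefined as an event. Capture is partial.
- **A decline table is not decisive either.** The contrast of 8 against 0 is the best case. Some placebo decline is plausible in a disease that progresses, and by 2 placebo decliners p is already 0.098. This stands against any claim that such a table would prove harm. Its purpose in a descriptive safety analysis is to make decliners visible.

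**Conclusion.** The point holds for Section 11.6.4 as written. It specifies no change from baseline for audiometry, its only categorical measure does not respond to a purely sensorineural loss, and no planned table counts subjects whose hearing declined.

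The consequence is limited to the audiometry tables and to a small minority of subjects, roughly 5-20%. At 10% affected with a 20 dB loss, the signal in the by-visit means is about 0.5-0.8 SE. The claim weakens towards the top of that range: 20% losing 30 dB with an SD of 15 dB would cross the yardstick about 60% of the time, and a large loss in 30-40% could well move the means. All of these sizes rest on assumed SDs, because the documents give none. That the gap does not move, and that no change analysis is named, does not depend on them.

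A reader might also take the 10, 15 and 20 dB figures elsewhere in the protocol as ready-made decline criteria. They are not. They define an air-bone gap (11.6.4), a between-frequency difference and a between-ear difference (inclusion criterion 4), not worsening within a subject.

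The primary analysis and the data collection are unaffected. The change is worth making because the better summary is available from data already planned.

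**What to change.** In Section 11.6.4, and in the SAP before unblinding, add by treatment group, visit and treated or untreated ear:

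1. Per-subject change from the pre-dose Visit 2 baseline in air and bone thresholds at each frequency and in PTA.
2. Number and percent of subjects whose hearing worsened from baseline by at least a pre-specified amount, with the cut-off or cut-offs chosen and justified by the sponsor.

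Keep the air-bone gap table for conductive change.

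The cost is a little extra programming. The audiograms are already scheduled at every visit in both ears, so there is no new procedure. Type I error is unaffected because the safety analysis is descriptive.

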11.6.5. Tympanometry

Shift tables representing the proportion of subjects with changes in their tympanogram from baseline to each post-baseline study visit will be calculated for each treatment group. Tympanogram changes will include both the type of tympanogram (A, B-small volume and/or normal, B-large volume, or C), as well as, whether the tympanogram was judged to be normal or abnormal.

11.6.6. Columbia- Suicide Severity Rating Scale (C-SSRS)

The C-SSRS will be administered at each visit using the appropriate version i.e. Baseline or Since Last Visit. Analysis of this scale will be performed on the Safety Analysis Set.

11.6.6.1. Baseline Version

The Baseline version of the C-SSRS will be administered at the Screening visit (Visit 1). This version of the scale captures both suicide ideation and suicide behavior (lifetime). There are 5 suicidal ideation questions, each captured as yes/no for the subject's lifetime. Additionally a sixth suicidal ideation variable will be created to indicate if there was any ideation, regardless of type. There are 4 suicidal behavior questions, each captured as yes/no for the subject's lifetime. A fifth suicidal behavior variable will be created to capture if there was any suicidal behavior regardless of type. An additional question asks if suicidal behavior is present during the visit. All suicidal ideation and behavioral variables as outlined here will be tabulated overall and by treatment group. All C-SSRS data will be included in data listings. There is no inclusion or exclusion criterion associated with the Baseline C-SSRS score. Subjects with a positive score should be referred to their primary care provider for follow-up.

11.6.6.2. Since Last Visit Version

The Since Last Visit version of the C-SSRS will be administered at each study visit after the Screening visit (Visit 1). The same overall individual variables for suicidal ideation and behavior will be assessed as in the Baseline version. In addition, overall suicidality (yes/no) will be defined as any subject having any suicidal ideation or behavior since the last visit. All suicidal ideation and behavior variables will be tabulated overall and by treatment group for each study visit. All C-SSRS data will be included in data listings.

Any subject with an appearance of any new suicidal ideation or suicide behavior since Screening should be referred to their primary care provider for follow-up.

If a subject has any post-Screening C-SSRS score of 1-3 for Ideation (i.e., a "yes" answer to Questions 1, 2, or 3) or a "yes" response to the Non-Suicidal Self-Injurious Behavior question) and the score is higher than the Screening C-SSRS score, then this assessment should be

recorded as an AE. This information is reported as indicated in Section 9.2.1. (Possible AE terms: Suicidal plans, Suicidal ideation, Suicidal tendency, Suicidal behavior, Suicidal intention, Suicidal depression, Active suicidal ideation, Passive suicidal ideation, Self-injurious behavior without suicidal intent).

If a subject has any post-Screening C-SSRS score of 4 or 5 for Ideation (i.e., a "yes" answer to question 4 or 5) and/or any questions answered yes for Suicidal Behavior (with the exception of a "yes" response to the Non-Suicidal Self-Injurious Behavior question), and this was not observed at Screening, then this assessment should be recorded as a Serious Adverse Event. This information is reported as indicated in Section 9.2.2.

11.7. Handling of Missing Data, Subject Withdrawals, and Treatment Failures

In addition to the primary analysis of the primary endpoint, if needed several sensitivity analyses will also be evaluated. These analyses will be included in the SAP with appropriate details prior to unblinding the database.

The SAP will include greater detail regarding the handling of missing data as well as the algorithms for scoring the SF-36, including the handling of missing questionnaire items.

Every effort will be made to follow subjects for study observation and encourage compliance with study measurements to minimize the amount of missing data.

Except for partial dates, safety data will not be imputed. The imputation algorithm for partial dates will be defined in the SAP.

11.8. Interim Analyses

There are no formal interim analyses planned. Blinded reviews of safety data will be conducted as described in Section 14.7; however, the review of such data is not intended to impact the study conduct unless there are safety concerns. As such, it is expected that the trial will continue to its scheduled completion barring any unexpected safety issues.

12. STUDY DRUG INFORMATION

12.1. Physical Description of Study Drug(s)

The investigational drug product administered to subjects in this study will be OTO-104 and placebo. The OTO-104 final product suspension for dosing will be prepared from two separate components, OTO-104 Diluent (one vial needed) and OTO-104 Active (one vial needed). An appropriate volume of OTO-104 Diluent will be withdrawn and delivered into the OTO-104 Active vial to achieve a visually homogeneous suspension of a target drug concentration of 60 mg/mL. Placebo will consist of the vehicle used to formulate OTO-104 and will be supplied from one vial (OTO-104 Diluent).

The following drug supplies will be used in the study:

Product	Supplied as:
OTO-104	A kit containing: one vial of OTO-104 Active and one vial of OTO-104 Diluent.
Placebo	A kit containing: one vial of OTO-104 Diluent.

12.2. Directions for Use

OTO-104 and placebo will be prepared by an unblinded QMP in a clean, secure location with a room temperature preferably at or below 23°C (73°F). The location will not be accessed by the blinded personnel during study drug preparation. Please refer to the Pharmacy Manual for detailed study drug preparation instructions.

12.3. Packaging and Labeling

12.3.1. Packaging

All study drug kits will be labeled with information that will meet the applicable regulatory requirements.

12.3.2. Labels and Labeling Instructions

A label will be affixed to each kit box indicating kit number and storage instructions. A label will be affixed to the OTO-104 Active and Diluent vials indicating contents and storage instructions. A syringe blinding label will be provided to mask the syringe contents for injection.

12.4. Management of Clinical Supplies

The clinical supplies will be managed by the IWRS. The IWRS will create shipment requests that will be generated based on inventory thresholds that are set for each site. A shipment request will be generated by the IWRS system and sent to the clinical supplies vendor. Upon shipment and receipt of the clinical trial material, the site personnel (e.g., pharmacy) will acknowledge the shipment using the IWRS and identify any damaged, missing, or unusable kits so they will not be dispensed.

12.4.1. Storage of Kits

All kits will be stored at 2-8°C, with allowable temperature excursions as high as 25°C for up to 72 hours. All temperature excursions of the study drug must be documented in the study drug accountability log. Any excursions within the allowable temperature range and conditions should be documented, but the study drug is still acceptable for use and dispensing to subjects. If any excursions are outside of these conditions, the study drug should not be used to treat subjects. If this occurs, the QMP preparing the study drug should immediately quarantine the product and report the kit(s) as unacceptable for dispensing to the IWRS to remove it from inventory.

12.5. Drug Accountability

It is the responsibility of the clinical investigator to ensure that all study drug received at the site will be inventoried and accounted for throughout the study and the result recorded on the drug accountability form maintained in the Pharmacy Manual. The QMP will be instructed to return all original containers, whether empty or containing study drug, when instructed by the study monitor to return. Study drug returned by the clinical site staff will be stored and disposed of according to the sponsor's instructions. Drug accountability will be verified by the sponsor's unblinded study monitor during the course of the study. Study drug will be stored in a limited access area or in a locked refrigerator under appropriate environmental conditions.

The investigator agrees not to supply the study drug to any person other than sub-investigators, designated staff and the subjects participating in the study. Study drug may not be relabeled or reassigned for use by other subjects except under special circumstances approved by Otonomy.

The investigator will retain and store all original containers returned by the clinical site staff until these containers are inventoried by the study monitor. Unless otherwise instructed by the sponsor, the investigator agrees at the end of the study to return all original containers, whether empty or containing study drug, to the sponsor as instructed by the study manager. The investigator agrees to neither dispense the study drug from, nor store it at, any site other than the study sites agreed upon with the sponsor.

The sponsor will ensure proper disposition of original containers empty or full with returned or unused study drug. Appropriate documentation will be maintained. Permission may be granted for local disposition, with supporting documentation.

13. ETHICAL ASPECTS

13.1. Investigator Responsibilities

The investigator is responsible for ensuring that the clinical study is performed in accordance with the protocol, the Declaration of Helsinki, as well as with the Note for Guidance on Good Clinical Practice (ICH/135/95), and applicable regulatory requirements. These documents set forth that the informed consent of the subjects is an essential precondition for participation in the clinical study.

13.2. Research Ethics Committee (REC)

This trial will be undertaken only after full approval of the protocol and addenda has been obtained from a designated REC and the sponsor has received a copy of this approval.

The REC must be informed of all subsequent protocol amendments issued by the sponsor.

Reports on, and reviews of, the trial and its progress will be submitted to the REC by the investigator at intervals stipulated in their guidelines.

13.3. Informed Consent

Each subject must give written consent (and sign other locally required documents) according to local requirements after the nature of the study has been fully explained. The consent form must be signed prior to performance of any study-related activity. The consent form that is used must be approved both by the sponsor and by the reviewing REC. The informed consent should be in accordance with the current revision of the Declaration of Helsinki, current International Conference on Harmonization (ICH) Good Clinical Practice (GCP) guidelines, and Otonomy policy.

The investigator must explain to potential subjects the aims, methods, reasonably anticipated benefits and potential hazards of the trial and any discomfort it may entail. Subjects will be informed that they are free not to participate in the trial and that they may withdraw consent to participate at any time. They will be told which alternative treatments are available if they refuse to take part, and that such refusal will not prejudice future treatment. Finally, they will be told that their records may be examined by competent authorities and authorized persons, but that personal information will be treated as strictly confidential and will not be publicly available. Subjects must be given the opportunity to ask questions. After this explanation and before entry into the trial, consent should be appropriately recorded by means of the subject's dated signature. If a subject is unable to read, an impartial witness must be present during the entire informed consent discussion. The signature of the impartial witness will certify the subject's consent. The subject should receive a signed and dated copy of the informed consent form.

